11. PRIVACY AND CONFIDENTIALITY

Data will be stored on a password protected HFH computer. Patient data will either be located in the chart or kept in a locked spreadsheet that contains no patient identification aside from a unique patient ID associated with their MRN. This will only be accessible to the investigators. Data will be destroyed following publication or after six months of inactivity. We will also obtain HIPAA authorization in order to access the medical record.

12. DATA AND SAFETY MONITORING PLAN

We will be consistently checking in on patients' safety as they undergo the usual post-operative RCR protocol. This will involve clinic visits in which we monitor the PT progress as well as the patient's adherence to the protocol. We will also be in weekly communication with therapists regarding patient progress and ability to complete protocol.

Unanticipated Problems and Adverse Events

We will report any problems or adverse events to the IRB via email

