3. STUDY PROCEDURES

- Patients who are seen in clinic for rotator cuff pathology will undergo treatment for their rotator cuff based

on a shared decision-making process with the orthopedic surgeon, irrespective of this study. Once a treatment plan is in place, the patient will be introduced to this study and presented with the opportunity to participate. If the patient agrees, a formal consent process will take place in clinic and the patient will undergo initial, baseline testing of strength, range of motion, pain scores, and patient reported outcome scores.

Therefore, patients will be either in the nonoperative arm or the operative arm of this study. Within each arm, patients will be randomized via computer to be placed in either the blood flow restriction (BFR) cohort or the traditional (non-BFR cohort). Patients will prospectively undergo rotator cuff rehabilitation using BFR or conventional therapy by physical therapists with extensive experience in rotator cuff rehabilitation who will undergo training on use of BFR.

The nonoperative group will be given identical rehabilitation protocols, with the only difference being the use of a BFR cuff during rehabilitation for the BFR cohort. Similarly, the operative group will be given identical rehabilitation protocols, with the only difference being the use of a BFR cuff during rehabilitation for the BFR cohort.

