Patients undergoing operative rotator cuff repair (RCR) will undergo preoperative rehabilitation prior to surgery for two weeks. Due to limitations of health insurance coverage of physical therapy sessions, the two weeks of preoperative "prehab" will consist of a structured home exercise program that is taught to the patient by a physical therapist during one session and recorded on a physical therapy (PT) diary by the patient during the two weeks leading up to surgery. Patients will be provided with video instruction and training on how to conduct the exercises and this will also be done with and without the use of BFR depending on group allocation (via randomization). Additionally, warning signs for BFR cuff intolerance such as increased pain, swelling, numbness/tingling of the arm will be communicated to the patient. Following surgery patients will immediately be started in a formal physical therapy regimen as an outpatient. Therapy will consist of a structured program progressing from range of motion to strength training and then functional tests. Patients will remain in their allocated BFR or non-BFR group.

Protocol as follows, both groups will use the same protocol with the only difference being use of BFR:

For surgical patients:

- Preop: Patients will undergo a home program consisting of isometric exercises including shoulder extension, abduction, external rotation and internal rotation pushing against a wall.

For both surgical and non-surgical patients:

- Post-op weeks 0-8: Passive shoulder range of motion (ROM) only
- Sling immobilization with active elbow, wrist and hand ROM
- Passive ROM only of shoulder including pendulums, supine elevation in scapular plane, external rotation with arm at side.

8-12 weeks being more active range of motion

- Discontinue sling
- Being active exercises including prone row, standing internal/external rotation with bands, wall slides into shoulder flexion

Weeks 12-20: Strength and function of Side lying shoulder external rotation, increase resistance band exercises

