Throughout this protocol patients will have a pre-operative visit, an early 2 week post operative visit to check range of motion and wound healing, a six week visit to monitor range of motion and potentially clear for active ROM and sling discontinuation, and a three month visit prior to clearance to being return to more aggressive activity. Strength and range of motion will be recorded at each of these visits in order to assess the primary endpoint.

Outcomes:

Primary Outcome:

- Strength to be measured via dynamometer at each clinic visit

Secondary Outcomes:

- Range of motion via goniometer
- Pain via visual analogue scale (VAS) pain scale at each visit
- Patient reported outcomes scores at each visit
- Fatty infiltration and muscle atrophy measured via ultrasound and compared to pre-operative imaging

Plan to recruit patients starting in June 2020. Will enroll patients and collect data from June-2020 to May 2021. Manuscript writing and submission to occur in June 2021.

Data analysis: The primary endpoint of this study was a maximum repetition total work deficit of 15% between the BFR and control group as measured by dynamometer. This was based on previous data showing that a strength deficit of 15% represents a clinically significant difference that is not likely attributable to limb dominance. Work deficit was calculated in each group by comparing the operative leg with the nonoperative leg to obtain a deficit percent. A power analysis was performed before the study to assess the number of patients needed to detect a 15% total work deficit between the BFR and control groups. With a power of 80% (beta level $\frac{1}{4} 0.80$, alpha level $\frac{1}{4} 0.05$), a sample size of 34 (17 patients per group) was obtained. Data will be provided to and analyzed by trained statisticians to determine differences in primary and secondary outcomes.

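### Section 12 describes active safety checks only for the post-operative protocol, so the two-week pre-operative home BFR programme has no scheduled safety contact or diary review

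*Combined protocol and SAP*

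**What the plan says.** Section 12 describes active monitoring of patients' "safety as they undergo the usual post-operative RCR protocol". It names two means: clinic visits that look at therapy progress and adherence, and weekly communication with the therapists.

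Section 3 (Study Procedures) gives operative patients two weeks of rehabilitation before surgery. It is a "structured home exercise program that is taught to the patient by a physical therapist during one session", and it is "recorded on a physical therapy (PT) diary by the patient during the two weeks leading up to surgery". Video instruction is provided, and "this will also be done with and without the use of BFR depending on group allocation". The safeguard specific to this phase is that "warning signs for BFR cuff intolerance such as increased pain, swelling, numbness/tingling of the arm will be communicated to the patient". Supervised therapy comes later: "Following surgery patients will immediately be started in a formal physical therapy regimen as an outpatient".

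On visits, Section 3 says "patients will have a pre-operative visit, an early 2 week post operative visit to check range of motion and wound healing", followed by visits at six weeks and three months. It does not date the pre-operative visit. The purpose it gives for recording at the visits is strength and range of motion.

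Other provisions also cover the home phase:

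- Section 9 gives patients contact information for questions throughout.
- Section 10 asks patients and other providers to report concerns. It withdraws anyone who cannot tolerate BFR, and withdraws immediately anyone with a complication. It also ends data collection on withdrawn patients and destroys their data.
- Sections 2 and 4 exclude higher-risk patients, including those with neurovascular injury, peripheral vascular disease, or a personal or family history of DVT.

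**The concern.** For an operative BFR patient, exposure to the cuff starts before the active monitoring that Section 12 describes. In the first two weeks the patient applies the cuff alone, having been taught once. Section 1 itself notes that evidence on pre-operative use is lacking, and Section 4 lists pain, nerve injury and swelling as harms of prolonged tourniquet use.

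The Section 10 rule on immediate withdrawal can act only on problems that reach the investigators. In the home phase it depends on the patient recognising a symptom and volunteering it, or on a provider who happens to hear of it. A patient who puts up with numbness, swelling or pain could keep using the cuff until the next contact, which as written may be surgery. The diary could bring this to light, but nothing says who reads it or when.

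**Working it through.** The plan gives no figure to reproduce. The check compares the timing of exposure with the timing of monitoring, then counts days.

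**1. Contacts described in the home window**

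| Possible contact | Where | Does it schedule a safety check in the two weeks? |
|---|---|---|
| Clinic visits for safety | Section 12 | Tied to the post-operative protocol |
| Weekly communication with therapists | Section 12 | Not expressly limited to the post-operative period, but the only therapist contact with the patient described in this phase is the teaching session |
| Pre-operative visit | Section 3 | Undated, with no safety check or diary review assigned |
| PT diary | Section 3 | Kept by the patient; no review or collection stated |
| Contact information, request to report | Sections 9 and 10 | Relies on someone volunteering the problem |

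The pre-operative visit may well be the consent and baseline visit. Section 3 says "a formal consent process will take place in clinic and the patient will undergo initial, baseline testing of strength", and Section 9 places consent at a pre-operative clinic visit. That would put it before home BFR starts, although a later date remains possible.

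**2. Longest stretch without described contact**

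Take day 0 as the teaching session (assumption) and day 14 as surgery, from the stated two weeks.

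- As written: 14 - 0 = 14 days.
- If the pre-operative visit falls mid-window (assumption): 14 / 2 = 7 days.
- With calls on exactly days 3 and 8: gaps of 3, 8 - 3 = 5 and 14 - 8 = 6, so 6 days.
- Allowing a day either side (first call on days 2 to 4, second on days 7 to 9): at worst 9 - 2 = 7 or 14 - 7 = 7 days. At best, with calls on days 4 and 9, the gaps are 4, 5 and 5, so 5 days.

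**3. Size of the window**

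Section 3 gives a power-analysis sample size of 34, 17 per group. It does not say whether 34 is an enrolment cap, or how patients divide between operative and nonoperative treatment.

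- All 34 operative: 17 x 14 = 238 BFR patient-days; 34 x 2 = 68 calls.
- Half of them operative (17, so 8 or 9 on BFR): 8 x 14 = 112 to 9 x 14 = 126 BFR patient-days; 17 x 2 = 34 calls.
- Staff time for 68 calls at an assumed 5 to 10 minutes each: 340 to 680 minutes, or 5.7 to 11.3 hours.

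If more than 34 are enrolled, these figures rise in proportion.

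**4. What withdrawal at the first warning sign would cost**

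This bears on how the remedy is worded. For a two-sided t test at the 5% level, 17 against 17 gives 80% power at a standardised difference of about 0.99. Holding that difference fixed:

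- losing 3 BFR patients (14 against 17) gives about 76% power;
- losing 5 (12 against 17) gives about 72%.

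The losses would fall only in the BFR group and would be related to tolerance, so selection bias would matter more than the lost power.

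**The case against.** The best case on the other side is that the pre-operative phase is already inside the plan and only loosely worded. The sentence on weekly therapist communication is not confined to the post-operative period and covers ability to complete the protocol. The exercise protocol in Section 3 begins with the pre-operative home programme, and the visit schedule includes a pre-operative visit. The diary is a natural adherence record. This has force: it would be wrong to say that the therapist communication cannot cover the home phase. What stands is that no contact is described from which a therapist would learn how the patient is doing, and no safety task is attached to the visit or the diary.

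A second objection is that the gain is uncertain. If the pre-operative visit falls mid-window, the longest gap is already 7 days and the calls may add nothing. Across the assumptions the improvement runs from 0 (7 to 7 days) to 9 days (14 to 5). That is correct, and it is one reason for a modest priority. The call days are also a judgement, not something derived from the documents.

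A third objection is that active questioning could harm the trial. Increased pain is plausible in anyone doing isometric exercise with a torn cuff. If every warning sign led to withdrawal under Section 10, only BFR patients would be removed and their data destroyed. This objection stands, and the remedy has to be worded to avoid it.

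A reader might also infer a 28-day gap, because the first dated clinic visit is two weeks after surgery. The documents do not support that: surgery is itself a contact, and formal therapy starts immediately afterwards.

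**Conclusion.** The point holds as a gap in active, scheduled monitoring. Section 12 describes its safety checks for the post-operative protocol, and the available text schedules no safety contact or diary review during the two weeks of home BFR. The 14-day gap assumes that the pre-operative visit comes before the teaching session. The 238 patient-days also assume that 34 is the total enrolled and that all are operative. These figures measure time without contact, not harm.

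A reader might infer that home users are left without safety provision, or that they face a known excess of complications. Neither follows. Taught warning signs, contact details, a reporting request, a withdrawal rule and relevant exclusions all apply at home. Section 4 describes complications as very rare and cuff use as very short, and the documents give no event rate for home use. The available text also lacks whatever stood between Sections 12 and 14, and practice may go further than the text. Confidence is medium and priority minor to moderate.

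**What to change.** Add to Section 12:

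> For operative patients, safety monitoring begins at first BFR use, including the pre-operative home programme. Existing study personnel will phone every operative patient, in both groups, about day 3 and about day 8 after the teaching session, with the same questions on pain, swelling and numbness/tingling, and will review the PT diary, which records these symptoms in both groups. A warning sign in a BFR patient pauses home BFR and prompts same-day clinical assessment; BFR is stopped for good only if intolerance or a complication is confirmed, and the patient's outcome data are retained and follow-up continues.

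The last clause also requires changing Section 10, so that stopping BFR no longer ends data collection or leads to destruction of the data. Section 3 should state when the pre-operative visit falls relative to the teaching session.

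Calling both groups keeps contact equal, in line with the plan's intention that BFR is the only difference between them. Section 3 attributes the home format to limits on insured therapy sessions; calls by study personnel use none.

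The cost is one amendment, a short call script, three diary fields and, under the assumptions above, at most 68 calls (about 6 to 11 hours). No clinic visit is added. The downsides are minor staff time and patient burden, possibly higher home-exercise adherence in both groups, and possibly more or earlier BFR discontinuations.
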